The W&W has gained great interest, as it provides the possibility to cure the patients without the need of major surgery and its consequences on functional outcomes and lifelong morbidity, and thus preventing overtreatment. However, this treatment concept is currently regarded as experimental and has not yet become part of commonly accepted guidelines. There is a need to increase the knowledge on the concept of cCR and CR in a population based patient cohort with a standardized treatment algorithm and follow-up.

Aim of the study

The aim of this study is to estimate the rate of regrowth among patients with locally advanced rectal cancer treated with neoadjuvant treatment with radiotherapy or chemoradiotherapy, where complete clinical response has been obtained, and thus to determine the positive predictive value of cCR in a national cohort.

Objectives and endpoints

Primary endpoint is the *rate of regrowth* among patients with cCR who follow the W&W protocol after preoperative radiotherapy or chemo-radiotherapy, in order to determine the positive predictive value of cCR.

Secondary endpoints are

- The rate of cCR after preoperative CRT
- To calculate the diagnostic accuracy of the clinical diagnosis of complete response
- The rate of metachronous distant metastases in patients following the W&W protocol
- The rate of metachronous metastasis and recurrence rate after ypCR
- Overall and cancer-specific survival of patients with cCR following the W&W protocol compared to patients with ypCR, i.e. patients with complete pathologic response after resection.
- Assess the rate of patients who otherwise would have had an APR
- Patient-reported outcome measures, such as Low anterior resection syndrome (LARS) and quality of life (QoL)
- To calculate the costs of treatment for W&W after cCR as compared to surgical treatment
- To assess the diagnostic accuracy of MRI in the diagnosis of complete response

Design

The current study is designed as an open prospective population-based study. All patients diagnosed and treated with radiotherapy or chemo-radiotherapy for rectal cancer in Norway will be eligible for this study, provided signed informed consent given before inclusion.

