All patients will be diagnosed according to national guidelines, and treatment decisions with regard to the need for neo-adjuvant chemo-radiation therapy will be made according to national guidelines in the setting of multidisciplinary team (MDT) meetings. Indication for preoperative radiotherapy or chemo-radiotherapy will follow up-to-date treatment guidelines at any time, and will not be extended to new groups of patients who are currently not offered neo-adjuvant treatment with the intention to achieve complete clinical response (cCR).

Patients who participate in the study will be followed closely according to a defined schedule as described below. Patients diagnosed with regrowth during follow-up will be scheduled for surgical resection as described below.

STROBE guidelines (23) form the base of the design of the study, as well as the analysis and publication of results. These guidelines intend to ensure best possible transparency of cohort studies, and helping to identify and report possible confounders that are inherent to this study design.

Inclusion criteria into the study

- Histologically verified adenocarcinoma of the rectum within 15 cm from the anal verge measured by rigid proctoscopy
- Patients who have completed neoadjuvant treatment according to national guidelines for rectal cancer, i.e., radiotherapy or chemo-radiotherapy (at least 40 Gy) or short-course radiotherapy combined with chemotherapy
- Patients aged ≥ 18 years of age are eligible for inclusion. However, patients aged ≤ 40 years are recommended to undergo surgery on the theoretical base of a possibly more aggressive tumour disease in this age group, and will be asked to participate in the study by consenting to recording of data. Those patients who insist on W&W approach after careful consideration and well-documented informed consent are eligible for entering the W&W protocol.
- Given informed consent
- Stage I-III rectal cancer; however, patients with limited liver metastases who undergo primary liver surgery as part of a "liver first" treatment approach may be included

The following patients will be offered inclusion into the Watch & Wait protocol

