Estimation of sample size is based on the aim of this study to detect the sensitivity (i.e., true positives) and specificity (i.e., true negatives), as well as 1-sensitivity (false positives) and 1-specificity (i.e., false negatives) in order to characterize the ability to correctly diagnose patients with cCR with a minimum of regrowth (i.e., false negatives) or unnecessary resections (i.e., false positives). Based on these estimations, it will be possible to achieve the primary endpoint of the study, i.e. the rate of regrowth, and to calculate positive predictive value of the diagnosis of cCR among patients who follow the W&W protocol after preoperative chemoradiotherapy.

As the present study is a prospective observational study, and not a clinical trial that aims to prove the superiority or non-inferiority of a specified treatment, power calculations that result in *numbers needed to treat or to harm*, do not apply here for the estimation of number of patients to include.

By including patients into the study who wish to undergo surgical resection despite the clinical finding of cCR, and decide not to follow the W&W algorithm, it will be possible to calculate these parameters based on a 2x2 table on the following assumptions based on results from current literature:

- During this time period, a tenfold/approx. 1000 patients will receive neo-adjuvant treatment
- Of those, 100 patients with cCR to enter the W&W protocol
- Of those 100, it may be assumed that
 - 85 will have a true CR
 - 15 will have ypCR (i.e., ypT0) after surgical resection
 - of those 100 patients, up to 30 may have regrowth after initial cCR within the W&W protocol
- Finally, 900 of 1000 (i.e., 870 patients + 30 patients with regrowth) will have ypT1-4 after surgical resection

Accordingly, the study aims to include at least 100 patients with cCR who choose to follow the W&W algorithm.

	True CR	No CR	
W&W (cCR)	True positive N=85	False positive N=30 (regrowth)	115
No W&W (No cCR)	False Negative N=15	True Negative N=870	885
	100	900	1000

Based on these figures, it will be possible to calculate sensitivity, specificity, 1-sensitivity, 1-specificity, positive and negative predictive values, positive and negative likelihood ratios, and perform ROC curve analysis.

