For analysis of the study, standard descriptive and analytic statistics will be applied when appropriate, and according to the distribution of the various variables. Multivariable analyses will be performed when appropriate with regard to relevant outcome variables, and in order to detect independent predictors of the outcome in question.

Survival analyses will be performed by Kaplan-Meier estimates and factors compared by using the log rank test. Multivariable analysis for time-dependent outcomes will be performed by Cox proportional Hazards analysis in order to detect independent predictors of the outcome in question.

The steering group has the necessary statistical knowledge and competency to provide appropriate statistic evaluation and analysis.

Organization

Patients with rectal cancer will be treated at all Norwegian hospitals that offer diagnosis and treatment for rectal cancer within the public specialist health service and according to national regulations and guidelines. When evaluation at 6 weeks after completed radiation indicates a possible full or near cCR, the patient will be referred to the cooperating University Hospital for further evaluation and recruitment to the W&W protocol when indicated, and informed consent will be obtained.

At each University Hospital, two dedicated colorectal surgeons will examine these patients, include in the W&W protocol and perform follow-up as described according to commonly agreed definitions. They will maintain the data entry forms and registration at the national registries.

In the case of equivocal or uncertain findings, these will be discussed in a collegial forum to achieve consent and decisions.

The W&W protocol will be referred to in the national guidelines as an ongoing study, and thus represent a treatment within a scientific study protocol. The study will be registered on public Norwegian websites such as <https://kliniskestudier.helsenorge.no>, and will be registered at clinicaltrials.gov.

Costs, finances and resources

The W&W protocol will be performed within the public specialist health care. Examinations that are part of the W&W protocol are mostly inexpensive clinical examinations or routine blood tests, with the exception of MRI examinations. However, the number of study participants is low, and as included patients will not need hospital consumptions related to surgery, the total economic load of the study is considered to be low.

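### The survival endpoint sets W&W patients selected on clinical response against operated patients selected on pathological response, so the groups differ in composition before any effect of treatment

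*Protocol*

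**What the plan says.** The protocol's Objectives and endpoints section fixes both groups: "Overall and cancer-specific survival of patients with cCR following the W&W protocol compared to patients with ypCR".

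Entry to W&W rests on a clinical judgement of complete response at about 6 weeks, or at about 12 weeks after an initial near-complete response (Response evaluation before enrolment in the study). The ypCR group is defined by the resected specimen.

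Study population and sample size gives the expected make-up of the W&W group. Of 100 such patients, "85 will have a true CR", and "of those 100 patients, up to 30 may have regrowth after initial cCR within the W&W protocol". The 2x2 table there puts the 30 regrowths in a W&W row of 115 and labels them false positives. The text also counts them among the 900 patients with tumour in the specimen. ypCR is described as follows: "15 will have ypCR (i.e., ypT0) after surgical resection".

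For analysis, Statistics states: "Survival analyses will be performed by Kaplan-Meier estimates and factors compared by using the log rank test". It adds Cox models to find independent predictors. Design refers to STROBE for confounders.

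Patients with cCR who decline W&W and choose surgery are to be asked for consent to be registered as controls, but the survival endpoint does not name them as its comparator.

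**The concern.** The two groups pass through different filters. A patient judged to have cCR who still harbours tumour stays in the W&W group. The same patient, if operated on, would be left out of the ypCR group once the specimen was read. One group is therefore a mixture of true responders and false positives, and the other contains responders only.

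This is the only listed endpoint that compares survival between W&W and surgery. Ethical considerations presents the study as a source of knowledge on W&W as an alternative to surgery. If a survival difference is reported, readers are likely to attribute it to omitting surgery, although part of it may come only from how the groups were formed. The comparator is fixed in the endpoint's wording, so this is not a detail left to a later analysis plan.

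**Working it through.** **1. The protocol's own figures** (Study population and sample size).
- Table margins: 85 + 30 = 115 in W&W; 15 + 870 = 885 not in W&W; 85 + 15 = 100 true CR; 30 + 870 = 900 without CR; total 1000. The margins add up.
- The text does not match the table. It has 100 W&W patients, but 85 true responders plus up to 30 regrowths is 115.

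**2. Share p of the W&W group that is not a true responder.**
- Text, regrowth line: up to 30/100 = 30% (an upper value).
- Table: 30/115 = 26.1%, so the positive predictive value is 85/115 = 73.9%.
- Text, true-CR line taken alone: (100 − 85)/100 = 15%. This is the lowest reading. The next line gives the number 15 to ypCR after resection, and the table places those 15 outside W&W.

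In the ypCR group the share with residual primary tumour is 0 by definition.

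**3. Shift from composition alone.** Suppose omitting surgery has no effect on survival. Let S_CR be survival of true responders in either group at a fixed time, and S_CR − gap that of patients with regrowth. Then:

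S_WW = (1 − p) × S_CR + p × (S_CR − gap)

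S_WW − S_CR = −p × gap

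The result does not depend on S_CR. The documents give no survival rates, so the gap is an assumption, shown as a range (all in percentage points):

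| p | gap 0 | gap 5 | gap 10 | gap 20 | gap 30 |
|---|---|---|---|---|---|
| 15% | 0 | −0.75 | −1.5 | −3.0 | −4.5 |
| 26.1% | 0 | −1.3 | −2.6 | −5.2 | −7.8 |
| 30% | 0 | −1.5 | −3.0 | −6.0 | −9.0 |

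As an illustration with an assumed S_CR of 90% and p = 30%: 0.7 × 90 + 0.3 × 80 = 87% at a gap of 10, and 0.7 × 90 + 0.3 × 70 = 84% at a gap of 20, against 90% in the ypCR group.

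**4. Whether the planned model removes it.** At given values of age and baseline stage, the W&W patients are still a mixture with some share p, and the ypCR patients still have share 0. Pathology is not known for W&W patients at entry, so it cannot be entered as a covariate for both groups. Neither the log-rank test nor a baseline-adjusted Cox model closes the difference.

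**5. The same check with a like-for-like comparator.** If operated cCR patients are taken whatever their specimen shows, both groups come from one selection rule and have the same expected p. The composition term is p × gap − p × gap = 0, before other confounding.

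**The case against.** The strongest case is that the direction is not established. A reader might infer that the comparison is biased against W&W by construction. The documents do not support that.

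- Ethical considerations says, on evidence it calls limited, that patients operated on for regrowth do comparably in local recurrence and survival. It does not say comparable to whom. At a gap of 0 the composition term vanishes. The same section, however, also lists a possibly worse outcome after regrowth surgery among the harms, so a zero gap cannot be taken for granted.
- Other imbalances act separately. The operated group carries surgical mortality, which the protocol acknowledges. Patients aged 40 or less are advised to have surgery because their disease may be more aggressive. Both could lower survival in the comparator.
- The ypCR group is not free of all disease. The sample-size section equates it with ypT0 and states no nodal condition.
- The study disclaims any aim to show superiority or non-inferiority, and this is one of nine secondary endpoints. To say the design defeats the endpoint's purpose would impute a causal purpose that the protocol does not state. Read as a benchmark against the best surgical responders, the comparison is legitimate.

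Two further inferences go too far. The plan is not an unadjusted log-rank test alone, since Cox models are also planned. The admission of liver-first patients is a study-level rule that may affect both groups, and it bears on the metastasis endpoints more than on this one. The protocol also fixes no time origin for survival; a statistical analysis plan may do so.

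These points limit the claim about direction and size. None of them answers the unequal selection, which is in the endpoint's wording and which the planned models cannot repair.

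**Conclusion.** The point holds as one of unequal selection. By the protocol's figures, 15% to 30% of the W&W group are not true responders, against no residual primary tumour in the ypCR group. With no treatment effect, this alone shifts W&W survival by −p × gap. The shift is nil if patients with regrowth survive as well as true responders. At assumed gaps of 10 to 20 points it is 1.5–3 points at p = 15%, 2.6–5.2 points at 26%, and 3–6 points at 30%, against W&W.

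The size rests on the assumed gap, on regrowth standing in for residual tumour, and on true responders having the same survival in both groups when treatment has no effect. The net direction of the whole comparison is not proven. What is established is that a difference, or the lack of one, between these groups cannot be read as the effect of omitting surgery.

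**What to change.** Amend the endpoint wording and add one analysis.

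- For any survival comparison meant to inform on omitting surgery, compare W&W patients with patients who met the final cCR criteria, declined W&W and had surgery, whatever their ypT stage. Keep them apart from the other registered controls, who had a near-complete response only, and from patients sent to surgery because digital examination or MRI suggested tumour.
- Start follow-up in both groups on the date cCR was declared.
- Use a Cox model adjusted for age and baseline stage as far as numbers allow, and report the estimate with its interval.
- Keep W&W versus ypCR as a descriptive benchmark. State the unequal selection beside it and give no causal reading.

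The cost is wording plus one analysis on patients whom the protocol already intends to ask for consent as controls. The downside is that the operated cCR group is self-selected, its size is not stated and it may be small, so the interval may be wide and some confounding will remain.

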- **Complete clinical response** at 6-8 weeks after neoadjuvant treatment includes two *negative signs*, i.e., the disappearing of the visible tumour leaving a flattening of the mucosa on the inner bowel wall, no tumour is seen, and the disappearing of any ulcer. These signs are *mandatory*. Two other criteria include *positive signs*, i.e., whitening of the previous tumour site appearing almost as a small white spot to merely a great area, and development of telangiectasia. These positive signs depend to a higher degree on time and individual interpretation, and are *not mandatory*:
 1. Flattening of the tumour site (mandatory)
 2. No ulcer visible (mandatory)
 3. Whitening of the tumour site (not mandatory)
 4. Visible telangiectasia (not mandatory)
- **Near Clinical Complete Response (near-cCR)** is defined as a nearly complete disappearance of the tumour and/or the ulcer of more than 75% at 6-8 weeks post RCT as determined by the clinician. A near-cCR may result in cCR after 11-12 weeks post CRT, and in this case the patient will be eligible for inclusion into the W&W

protocol at that time. Otherwise, the condition is not a cCR and surgery is offered immediately.

Patients with cCR after preoperative CRT who decline the W&W protocol and wish to undergo surgery, or patients with near, but not complete clinical response will be asked to give consent to participate for registration in the database as controls.

Exclusion Criteria

- Patients without cCR
- Patients unable to give informed consent
- Patients with short course radiotherapy (5x5 Gy) without additional chemotherapy, or patients receiving less than 40 Gy in long course CRT
- Patients with cCR but with increasing tumour growth on MRI after preoperative treatment
- Patients with metastatic disease at the time of diagnosis with the exception of those who are eligible for "liver first" treatment approach as part of an intention to cure approach.
- Patients previously diagnosed and treated for malignant disease in the pelvic region with radio- or chemoradiotherapy
- Other circumstances that may interfere with successful participation in the W&W protocol

Radiation and chemoradiation

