Neoadjuvant treatment will be given based on a decision by the MDT and according to national guidelines that apply at any given time during the study period. Preoperative radiotherapy is currently given as long course radiotherapy to 50 Gy with concomitant chemotherapy (capecitabine or 5-fluorouracil). Patients treated with short-course 5x5 Gy with combination chemotherapy are also eligible for participation. Neoadjuvant treatment with any modifications due to patient-related factors are acceptable as far as the effect of received treatment is considered to be at least 80% of standard treatment.

Response evaluation before enrolment in the study

All patients who receive preoperative CRT will be evaluated for treatment response at approximately 6 weeks after the last radiation treatment by MRI and clinical examination, including digital rectal examination (DRE) and rigid proctoscopy.

Patients with cCR (i.e., ycT0N0) will be invited for participation in the study.

Patients with near-cCR will be invited to undergo a second evaluation for cCR at 12 weeks for participation in the study. State of clinical tumour regress will be documented by endoscopic photography imaging when cCR is concluded. Patients with initial near-cCR, but without cCR at 12 weeks will be advised to undergo surgery according to current guidelines. The accuracy of DRE in cCR is not evident. When either DRE and/or MRI suggest a tumour in patients who otherwise fulfil cCR criteria, they are offered surgery and asked for inclusion into the study without W&W protocol.

Patients who fulfil the criteria for cCR as defined at 6 weeks or 12 weeks will be asked for participation in the W&W protocol. All other patients who were considered for cCR without a final diagnosis of cCR will not be eligible for the W&W protocol, but they will be asked to participate in the study by recording their data of treatments and outcomes in order to calculate the necessary statistics (e.g., sensitivity, specificity or likelihood ratios of possible prognostic or predictive factors for the study endpoints). These patients will be offered systematic follow-up as described in national guidelines.

Treatment course of the included patients and follow-up

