
An Adverse Event (AE) is any unfavourable and unintended sign (including a laboratory finding), symptom, temporally associated with the use of a medical treatment or procedure that may or may not be considered related to the medical treatment or procedure.

Grade refers to the severity of the AE. The CTCAE displays Grades 1 through 5 with unique clinical descriptions of severity for each AE based on this general guideline:

Grade 1	Mild; asymptomatic or mild symptoms; clinical or diagnostic observations only; intervention not indicated.
Grade 2	Moderate; minimal, local or noninvasive intervention indicated; limiting age-appropriate instrumental activities of daily life
Grade 3	Severe or medically significant but not immediately life-threatening; hospitalization or prolongation of hospitalization indicated; disabling; limiting self care activities of daily life
Grade 4	Life-threatening consequences; urgent intervention indicated.
Grade 5	Death related to AE.

Serious adverse events (SAE, grade 3-5 AE) will be recorded in the CRF and reported to the steering group of the trial:

- Description of event
- Time of first symptoms
- Severity: Evaluation of degree
- Relation to investigation (probable, improbable, uncertain)
- Action taken or planned for investigation
- Time of abatement/stabilization of condition

The steering group will decide on possible consequences for the trial.

International collaboration

In addition to the current national protocol, an international collaboration has been established to collect a large international database of patients who undergo a W&W treatment after cCR – the **International Watch & Wait database** (<http://www.iwwd.org>). Every Norwegian institution has the opportunity to provide the IWWD with its own data, and on its own initiative and responsibility.

Study population and sample size

The study population is intended to include most, and ideally all, patients who undergo neo-adjuvant treatment for rectal cancer and achieve a cCR and/or ypCR during the study period. Annually about 50 patients are registered at the CRN/NCCR database in Norway with ypCR after long course radiotherapy with or without concomitant chemo sensitization.

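### The exclusion list has no stated scope and enrolment reaches only suspected responders, so the 885 test-negatives behind the secondary accuracy measures are not secured

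*Protocol*

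**What the plan says.** **Exclusions.** The Exclusion Criteria section names "Patients without cCR" and "Patients with cCR but with increasing tumour growth on MRI after preoperative treatment". The heading carries no scope. The matching inclusion list is headed "Inclusion criteria into the study", which suggests study level. The last exclusion bullet, "Other circumstances that may interfere with successful participation in the W&W protocol", suggests W&W level.

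**Who else may join.** Design makes every patient treated with radiotherapy or chemoradiotherapy for rectal cancer in Norway eligible, given consent. Just before the exclusions, the Protocol says that "patients with near, but not complete clinical response will be asked to give consent to participate for registration in the database as controls". Response evaluation before enrolment in the study says: "All other patients who were considered for cCR without a final diagnosis of cCR will not be eligible for the W&W protocol". It then asks those patients to have their data recorded, so that sensitivity, specificity and likelihood ratios can be calculated. The same section asks patients who otherwise meet the cCR criteria, but in whom digital examination or MRI points to tumour, to join without W&W.

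**Intended population and table.** Study population and sample size aims at patients who "achieve a cCR and/or ypCR during the study period". Its 2x2 table covers 1000 treated patients and includes "True Negative N=870". From this table the Protocol plans sensitivity, specificity, both predictive values, both likelihood ratios and a ROC analysis.

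**The concern.** Specificity, NPV and the likelihood ratios all need patients in whom the test (the clinical diagnosis of cCR) is negative. The cCR rate needs all treated patients as its denominator. Diagnostic accuracy and the cCR rate are both named secondary endpoints, and the sample-size section is built around sensitivity and specificity.

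An exclusion that sites could apply to every patient without cCR would empty the test-negative row. A looser reading fills it only with near-responders. The reported accuracy would then depend on how many near-responders each site happened to recruit. A later analysis plan cannot repair this, because eligibility and consent decide which data exist.

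**Working it through.** **1. The Protocol's own table.** Inputs (Study population and sample size): TP 85, FP 30, FN 15, TN 870. The margins agree: 85 + 30 = 115; 15 + 870 = 885; 85 + 15 = 100; 30 + 870 = 900; total 1000.

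- Sensitivity = TP/(TP+FN) = 85/100 = 85.0%
- Specificity = TN/(TN+FP) = 870/900 = 96.7%
- PPV = TP/(TP+FP) = 85/115 = 73.9%
- NPV = TN/(TN+FN) = 870/885 = 98.3%
- LR+ = sensitivity/(1 − specificity) = 0.85/(30/900) = 25.5
- cCR share = 115/1000 = 11.5%

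**2. Exclusion applied to the whole study.** FN = TN = 0. Specificity is 0/30, sensitivity 85/85, NPV 0/0 (undefined) and the cCR share 115/115 = 100%. Only PPV survives, at 73.9%.

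**3. Exclusion read as W&W entry only.** The question is then which test-negatives the procedures reach.

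- The opening text on participating hospitals speaks of including patients with possible complete or near-complete response.
- Response evaluation limits recording to patients who had been considered for cCR.
- Organization refers patients to the University Hospital, where consent is taken, only when the 6-week evaluation suggests a full or near response.
- Study population and sample size says the table becomes calculable by including cCR patients who decline W&W. Those patients are test-positive and cannot fill a No-cCR row.

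No step asks clear non-responders for consent.

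**4. Size.** Let n be the number of enrolled test-negatives. The Protocol gives no figure for n, so 50, 100 and 200 are assumptions. Keep TP 85, FP 30 and all 15 FN, so that TN = n − 15 and sensitivity stays at 85%.

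| n | Specificity | NPV | LR+ | cCR share of enrolled |
|---|---|---|---|---|
| 50 | 35/65 = 53.8% | 35/50 = 70.0% | 0.85/(30/65) = 1.8 | 115/165 = 69.7% |
| 100 | 85/115 = 73.9% | 85/100 = 85.0% | 0.85/(30/115) = 3.3 | 115/215 = 53.5% |
| 200 | 185/215 = 86.0% | 185/200 = 92.5% | 0.85/(30/215) = 6.1 | 115/315 = 36.5% |
| 885 (table) | 870/900 = 96.7% | 870/885 = 98.3% | 25.5 | 11.5% |

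Even if half the true negatives were enrolled (435), LR+ would be 0.85/(30/465) = 13.2, about half the planned value.

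**5. If false negatives are missed as well.** Pathological complete responses among clear non-responders would go unseen. Take n = 100 with only 5 false negatives (assumed): sensitivity 85/90 = 94.4% and NPV 95/100 = 95.0%, against 85.0% for both with all 15. So this gap raises sensitivity and NPV, while the loss of true negatives lowers specificity and LR+. The net error in NPV has no fixed direction.

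**6. Primary endpoint.** PPV = 85/115 does not involve the No-cCR row and is 73.9% in every scenario.

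**The case against.** The strongest reply is that the list was meant for W&W entry. It follows the block on who is offered W&W, its last bullet mentions W&W, and reading it that way reconciles it with the controls and with the patients recorded in order to calculate accuracy. That is a fair reading and probably the intended one. A reader might infer from the bare list that specificity, NPV and likelihood ratios cannot be obtained at all. The text does not support this, except when the list is applied literally to the whole study.

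A reader might also infer that the MRI exclusion removes the cell needed to judge MRI accuracy. It does not. The response-evaluation section keeps patients in whom MRI suggests tumour, and the exclusion bullet is narrower, since it concerns increasing growth. The two wordings overlap and need reconciling, but only a subgroup is ambiguous.

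Nor is it right that the cCR rate has no denominator. All patients given preoperative CRT are to be evaluated, the collected variables include those of the mandatory registries, and the Protocol already takes its annual ypCR count from CRN/NCCR. The source exists but is not assigned this role: the coupling section concerns the study dataset and rests on patient consent.

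The broad eligibility sentence in Design and the stated wish to include ypCR patients also help the Protocol, but neither comes with a procedure for reaching clear non-responders. The gap in the 885 row therefore stands.

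**Conclusion.** The point holds in limited form. The exclusion list lacks a scope and, read study-wide, contradicts other sections. Read as W&W-only, it still leaves the No-cCR row to a selected group of near-responders.

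The statistics could be calculated, but they would not describe the treated population that the table assumes. With 50 to 200 enrolled test-negatives, specificity would be about 54% to 86% instead of 96.7%, and LR+ about 1.8 to 6.1 instead of 25.5. These figures rest on the Protocol's assumed cell counts, on assumed enrolment, and on all 15 false negatives being captured. They show sensitivity to recruitment and are not forecasts.

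Only secondary endpoints are touched. The regrowth rate and PPV are not, so this should be fixed but does not threaten the primary result.

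**What to change.** 1. State for each exclusion whether it governs the study or only W&W entry, and reconcile the MRI wording in Exclusion Criteria with that in Response evaluation. How the W&W entry rules themselves are settled is for the sponsor.
2. Define the accuracy cohort as all neoadjuvantly treated patients who meet the treatment criteria in the accrual period. Name CRN/NCCR as the source, as counts, of the No-cCR row (split by ypCR or not) and of the cCR-rate denominator. The Protocol expects to identify only 70% of eligible cCR patients, so say how cCR patients who are not enrolled will be kept out of the No-cCR row.
3. If such counts cannot be had, drop specificity, NPV and likelihood ratios for the whole treated population. Report PPV, plus accuracy explicitly restricted to patients with cCR or near-cCR.

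The cost is some eligibility wording and one registry extract, with no new patient procedures. The fallback costs narrower accuracy claims.
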